The HYPER study is the first to investigate hyperexcitability as a potential early driver of tumor progression in glioblastoma patients. If hyperexcitability is shown to contribute to tumor growth, future clinical trials should focus on targeting hyperexcitability to achieve tumor control. The overarching goal is to enhance overall survival.

b. Short review of literature:

Glioblastoma is the most common and aggressive primary brain tumor in adults¹. Treatment consists of maximal safe resection, radiotherapy, and chemotherapy. Despite this the median overall survival for glioblastoma is only 15 months².

Epilepsy is one of the most common symptoms in gliomas³⁻⁵. Glioma-related epilepsy (GRE) negatively impacts quality of life⁶. GRE treatment with anti-seizure medication (ASM) is given following the first epileptic seizure to achieve durable seizure control and improved quality of life.

In patients with epilepsy, the neurons are both firing too much and too synchronized. Hyperexcitability is a term used in this area of research to describe the excessive firing of neurons. Preclinical studies show that excessive firing between glioma cells and neurons drive glioma growth and invasiveness and that treatment with ASM inhibits tumor growth^{7,8}. A recent large epidemiological study found that patients with epileptic seizure after glioma diagnosis had a significantly poor prognosis⁹. Taken together these studies suggest hyperexcitability and GRE drive glioma growth and negatively impact survival in HGG patients.

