The HYPER study is an observational cohort study. There will be no control group, randomization, or use of placebo.

Hyperexcitability

To measure neuronal hyperexcitability in real-life settings, patients will undergo a scEEG.

Neuronal hyperexcitability will be defined as the presence of IEDs on the scEEG.

The scEEG will be inserted in the period from end of radiotherapy till first MRI evaluation after two cycles of adjuvant chemotherapy (Figure "Study flow"). Recordings from the device will start after implantation.

A specialized AI analytic software for managing long term EEG data will be used to highlight suspected IEDs that can be reviewed by a clinical neurophysiologist to determine if these episodes show epileptiform discharges^{11,12}.

Epilepsy

All patients who develop epilepsy will be treated at Rigshospitalet by [name], clinical professor in neurology with a special focus on epilepsy. Patients will be treated with standard treatment for epilepsy according to national guidelines¹³.

b. The practical implementation, examinations, and scope

Patients will be informed and included via the Department of Cancer Treatment at Rigshospitalet. Detailed inclusion process is described in section 13. The doctors and nurses at the department are experienced in including patients for clinical trials.

A neurosurgeon ([name], neurosurgeon at the Department of Neurosurgery, Rigshospitalet) will place a scEEG device under the skin behind the patient's ear closest to the tumor. The device is inserted under local anesthesia in 20 minutes. The electrodes can be inserted with different directions and will be positioned closest to the tumor.

The scEEG will be explanted after fifteen months with the possibility of extension in case the scEEG device is approved for longer implantation. The scEEG does not need to be removed before cremation.

Patients will have an extra visit at Rigshospitalet when the scEEG is implanted and one when it is explanted. Patients who develop epilepsy might have extra visits at Rigshospitalet in relation to treatment with ASM. Otherwise, there will not be extra visits needed for participation in the study.

c. Deviations from standard treatment

There will be no deviations from standard treatment both regarding tumor and epilepsy treatment.

4. Statistical considerations

a. Power analysis

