This study is explorative, and no studies have used scEEG to identify IEDs in brain tumor patients before. Therefore, making assumptions for power analysis is challenging since no data is available from similar study designs.

Our endpoints are development of epilepsy, seizure control, progression free survival and overall survival.

Based on current data from our clinical database the number of patients needed for this study is estimated to be fourteen patients. The level of significance is 2.5% one sided and the power 80%. The sample size is determined under the following assumptions: the proportion of patients having epilepsy is 50%, and the sensitivity for epilepsy with hyperexcitability is 85% or better. The null hypothesis is diagnostic accuracy = 0.5 against the alternative that diagnostic accuracy > 0.5.

5. The study participants

- a. Inclusion criteria:
 - Patients who have consented to the Neurogenom protocol¹⁴
 - Patients 18 years of age or older
 - Patients diagnosed with glioblastoma, IDH wild type grade 4
 - Patients treated with standard therapy at Rigshospitalet, Department of Cancer Treatment
 - Patient with a tumor located in a region where scEEG is expected to provide adequate signal quality
 - Performance status 0-1
 - Patients willing and able to use the scEEG, UNEEG EpiSight solution, day and night for the duration of the study
 - Patients willing and able to provide written informed consent
 - Patients able to understand the consequences of participation
 - Patients able to complete all study-required procedures, assessments and follow-up
- b. Exclusion criteria:
 - Patients who have a diagnosis of epilepsy
 - Patients treated with ASM
 - Pregnancy
 - High risk of surgical complications as assessed by the neurosurgeon
 - Involved in therapies with medical devices that deliver electrical energy into the area around the implant, such as cochlear implant(s), implantable brain stimulation and external/transcranial brain stimulation
 - Contraindications to the local anesthetic used during implantation and explantation

6. Risks, side effects, and disadvantages in the short and long term.

a. Safety measures that minimize pain, discomfort, fear, and other risks

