Patients have regular visits at the hospital during the six weeks of radio-/chemotherapy. During these visits, patients will be made aware about the study by nurses or doctors at the Department of Cancer Treatment. If the patient is interested in participation, they will be referred to the principal investigator or to one of the doctors who have received training in patient enrollment and have consequently been delegated the responsibility for including patients in the study. The trial participant and the principal investigator or delegated doctor will then meet at the Department of Cancer Treatment, and the trial participant will be informed about the study.

- c. Process of obtaining informed consent
 - i. Where, when, and who provides the oral and written information

The patient will receive written and oral information about the study either by the principal investigator or the delegated doctor. This visit is voluntary and will take place at the Department of Cancer Treatment.

All relevant doctors at the department will be trained in patient enrollment and consequently be delegated the responsibility for including patients in the study. The delegation log will be attached to this application.

The written and oral information will be given in the period from start of radio-/chemotherapy till first MRI evaluation after radio-/chemotherapy. See attached figure "Study flow".

- How it is ensured that the discussion takes place undisturbed Consultations with patients and their relatives will be in a private and undisturbed room during their visit to the Department of Cancer Treatment.
- iii. How the right to a companion is ensured The nurses and doctors at the department will tell the patients about the right to an accompanying person before the information meeting with the principal investigator or delegated doctor.

iv. The reflection period between receiving oral and written information and providing informed consent

The patients will have a right for >24 hours of reflection time.

v. When consent is sought

Consent is obtained once the patient has had sufficient time to reflect. Consent can be given to either the principal investigator or delegated doctor. Consent can be given eighter at the next scheduled visit to the department or at an extra visit.

14. Publication of results

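### The exposure rule and implant window let IEDs that follow regrowth count as hyperexcitability, so an association with PFS cannot show that hyperexcitability drives progression

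*Protocol*

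**What the plan says.** - **Implant window (section 3a).** "The scEEG will be inserted in the period from end of radiotherapy till first MRI evaluation after two cycles of adjuvant chemotherapy".
- **Start of measurement (section 3a).** "Recordings from the device will start after implantation". No earlier EEG is planned as a baseline.
- **Exposure (section 3a).** "Neuronal hyperexcitability will be defined as the presence of IEDs on the scEEG". The definition does not separate IEDs before progression from IEDs after it. Section 3b plans explantation after fifteen months, with possible extension.
- **Purpose (section 2a).** The study is described as the "first to investigate hyperexcitability as a potential early driver of tumor progression in glioblastoma patients". The same paragraph says that, if a contribution to tumor growth is shown, later trials should target hyperexcitability. Section 2b speaks of a causal relationship that patient data could confirm.
- **Endpoints (section 4a).** "Our endpoints are development of epilepsy, seizure control, progression free survival and overall survival". The table in section 8b lists the date of progression among the items to be correlated with hyperexcitability.
- **Eligibility (section 5).** The treatment criterion is "Patients treated with standard therapy at Rigshospitalet, Department of Cancer Treatment". None of the ten inclusion and six exclusion criteria mentions progression status.
- **Information to patients (section 13c).** This is given "in the period from start of radio-/chemotherapy till first MRI evaluation after radio-/chemotherapy", followed by more than 24 hours for reflection.

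**The concern.** To support a driver hypothesis, the exposure has to be measured before the outcome process it is meant to explain. Two stated rules prevent this.

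1. Implantation can fall on any day up to an MRI evaluation, in a patient whose tumor may already be growing again. If that MRI shows progression, the patient has a PFS event after perhaps only days of recording, and the regrowth was there before the first IED could be seen.
2. Exposure is any IED over the whole recording, so an IED that first appears after progression still classifies the patient as hyperexcitable.

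If regrowth itself provokes IEDs, both rules can produce a link between IEDs and short PFS without any driving effect. The protocol would use such a link to motivate trials that target hyperexcitability.

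**Working it through.** The protocol has no PFS calculation to reproduce. Its one sample size figure, 14, comes from the epilepsy accuracy test and does not enter here.

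**Step 1. Time order from the text.** Implantation can come late in the window (3a), recording starts afterwards (3a), no criterion excludes regrowth (5), and exposure has no cut-off at progression (3a). The sequence regrowth, implantation, first IED, progression on MRI is therefore allowed and would count as exposure followed by an event.

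**Step 2. How many patients.** Assumptions, none from the documents: a window of 12 weeks from end of radiotherapy with the MRI at its end, implantation uniform over the window, and exponential time to regrowth with median m of 20 to 40 weeks.

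- Regrowth by the MRI: 1 − 2^(−12/m).
  - m = 20: 1 − 0.660 = 34.0%, or 4.8 of 14.
  - m = 40: 1 − 0.812 = 18.8%, or 2.6 of 14.
- Regrowth before implantation: 1 − (1 − 2^(−12/m)) / (12 ln 2 / m).
  - m = 20: 1 − 0.340/0.416 = 18.2%, or 2.5 of 14.
  - m = 40: 1 − 0.188/0.208 = 9.7%, or 1.4 of 14.

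**Step 3. How this enters the comparison.** Assume IEDs are seen in 60% of patients with regrowth before implantation and in 30% of the others, with no effect of IEDs on progression. The share with regrowth already present is then:

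| m | Among IED-positive | Among IED-negative |
|---|---|---|
| 20 | 0.182×0.6 / (0.182×0.6 + 0.818×0.3) = 31% | 0.182×0.4 / (0.182×0.4 + 0.818×0.7) = 11% |
| 40 | 0.097×0.6 / (0.097×0.6 + 0.903×0.3) = 18% | 0.097×0.4 / (0.097×0.4 + 0.903×0.7) = 6% |

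The IED-positive group carries about three times the share of early PFS events, although IEDs cause none of them.

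**Step 4. Hazard ratios by simulation.** No true effect, medians 20, 30 and 40 weeks, MRI every 12 weeks. IED probability over the first four weeks of recording rises with regrowth from 30% to 60%, 40% to 70%, or 40% to 60%.

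| Set-up | PFS hazard ratio, IED-positive vs negative |
|---|---|
| Implantation spread over the window | about 1.1 to 1.5 |
| Only regrowth before implantation raises IEDs | 1.11 to 1.24 |
| Everyone implanted on day 0 | about 1.03 to 1.15 |
| Landmark at first MRI, progression-free patients, earlier IEDs only | 0.96 to 1.05 |

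The four-week period is an assumption. Under the protocol's own rule, any IED in 15 months, runs with low IED rates gave about 2 to 3. That figure is the least secure, because it depends on how long patients go on recording after progression.

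**Step 5. Precision.** With 14 events split evenly, the standard error of the log hazard ratio is √(4/14) = 0.535, so the 95% limits lie a factor exp(1.96 × 0.535) = 2.85 either side of the estimate. A false ratio of 1.5 is ln 1.5 / 0.535 = 0.76 standard errors.

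**The case against.** **This is material for the analysis plan.** Landmarks, time zero and analysis sets are commonly left to the SAP, which is not shown, and their absence is no fault. That stands for the details. But the exposure definition, the window, the eligibility criteria and the causal purpose are all stated in the protocol, and together they permit the wrong time order.

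**The size is assumed, and small against noise.** This stands. Window length, medians and IED rates are not in the documents, and the bias is below one standard error in the four-week scenarios. Part of it remains even with everyone implanted on day 0, so the window is not the only source. The study is exploratory, and its only stated test concerns epilepsy.

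**A landmark brings its own problem.** Recording time before the MRI would vary with implant date. At a constant 30% to 40% chance of an IED per four weeks, one week of recording gives 1 − 0.7^(1/4) = 9% to 1 − 0.6^(1/4) = 12% IED-positive, and 12 weeks gives 1 − 0.7³ = 66% to 1 − 0.6³ = 78%. This stands, and the remedy has to allow for it.

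**Stronger readings that the text does not support.**
- A reader might infer that documented progression precedes recording. The window in section 3a closes at the MRI, so progression first seen there is dated on or after implantation. Only undetected regrowth is shown to come earlier.
- A reader might take this MRI to be the first assessment of progression. The protocol does not say so, and the study flow figure is not available. If the MRI in section 13c is an earlier scan, documented progression before implantation becomes possible. If it is the same scan, a patient informed at that point could not be implanted within the window.
- A reader might assume that the bias always favors the hypothesis. If recording ends early, for example at death, patients with long PFS have more time to show an IED, which pulls the other way.

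**Conclusion.** The concern holds in a limited form. As written, IEDs that follow undetected regrowth or progression count as exposure, so an association with PFS cannot establish that hyperexcitability drives progression. This follows from the text and needs no assumption about numbers.

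The size does need assumptions. With a 12-week window and median regrowth of 20 to 40 weeks, about 1 to 3 of 14 patients have regrowth before implantation. If IEDs are judged over four weeks, the false hazard ratio is about 1.1 to 1.5. Under the any-IED rule it could be larger, and its direction depends on how long recording continues.

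The epilepsy endpoint and the sample size of 14 are not affected. The change is worth making before enrolment, because progression status at implantation is best recorded at the time.

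**What to change.** Leave enrolment and the epilepsy analysis as they are. For PFS and the driver question, state in the protocol that:

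1. progression status is recorded at implantation;
2. the landmark is the first MRI evaluation after implantation, and the main comparison includes only patients progression-free at it;
3. PFS is counted from that MRI;
4. only IEDs recorded before it are used, expressed per unit of recorded time or subject to a stated minimum recording time, so that exposure does not simply reflect the implant date;
5. patients with progression at or before that MRI are described separately;
6. an analysis of all patients from implantation is given as a sensitivity analysis.

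Sections 3a and 13c should also be reconciled so that it is clear whether they mean the same MRI.

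The cost is mainly wording, since MRI and date of progression are already collected. About 3 to 5 of the 14 patients, under the assumptions above, leave the main PFS comparison. It stays imprecise and exploratory. The landmark removes the bias only as far as the MRI detects regrowth.

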In clinical practice, hyperexcitability can be measured with electrodes placed on the scalp called electroencephalogram (EEG). An EEG from a patient with epilepsy can reveal specific hyperexcitable electric patterns described as interictal epileptic discharges (IEDs)¹⁰. In contrast to the standard 30-minute scalpEEG, a novel device has been developed by a Danish company (UNEEG) to continuously monitor electrical activity using electrodes under the skin (subcutaneous EEG (scEEG))¹¹. The device is CE marked and we will use it as an instrument to continuous, long-term, EEG monitoring to improve the detection of IEDs and seizure activity compared to routine 30-minute EEG. Routine EEG often fails to capture transient abnormalities due to its short duration, leading to missed diagnoses. In contrast, scEEG enables prolonged recording, increasing sensitivity to rare events and providing a more comprehensive assessment of seizure patterns. Additionally, scEEG improves diagnostic accuracy in

patients with infrequent seizures, allowing for treatment optimization. Its minimally invasive nature makes it suitable for outpatient settings, enhancing patient comfort and compliance while reducing hospitalization needs. Thus, this device enables continuous investigation of hyperexcitability as part of epilepsy and tumor development – this causal relationship has only been studied in laboratory experiments. Knowledge from patients could confirm and shed light on this disease mechanism, potentially leading to better treatment. A video about the scEEC can be found via

treatment. A video about the scEEG can be found via the QR code, or via this link: https://vimeo.com/1006556953?share=copy.

References:

- 1 Ostrom, Q. T. *et al.* CBTRUS Statistical Report: Primary Brain and Other Central Nervous System Tumors Diagnosed in the United States in 2016-2020. *Neuro Oncol* **25**, iv1-iv99 (2023). https://doi.org/10.1093/neuonc/noad149
- 2 Stupp, R. *et al.* Radiotherapy plus concomitant and adjuvant temozolomide for glioblastoma. *N Engl J Med* **352**, 987-996 (2005). https://doi.org/10.1056/NEJMoa043330
- 3 Mahaley, M. S., Jr. & Dudka, L. The role of anticonvulsant medications in the management of patients with anaplastic gliomas. *Surg Neurol* **16**, 399-401 (1981). https://doi.org/10.1016/0090-3019(81)90227-5

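### No masking is stated for the IED reading that the sized test depends on, and nothing keeps the IED findings out of the epilepsy diagnosis

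*Protocol*

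**What the plan says.** - **Predictor.** Section 3a: "Neuronal hyperexcitability will be defined as the presence of IEDs on the scEEG". Software flags suspected IEDs, which can then be "reviewed by a clinical neurophysiologist to determine if these episodes show epileptiform discharges". The section does not say what the reader knows about the patient's clinical course.
- **Second use of the recording.** Section 2b says the study will use the device "to improve the detection of IEDs and seizure activity compared to routine 30-minute EEG". The same paragraph makes a general statement about the device: "Additionally, scEEG improves diagnostic accuracy in" "patients with infrequent seizures, allowing for treatment optimization".
- **Outcome and test.** Section 4a lists development of epilepsy first among four endpoints. It sizes the study at fourteen patients for a test of diagnostic accuracy 0.5 against more than 0.5, one-sided 2.5%, power 80%, assuming 50% with epilepsy and sensitivity of 85% or better.
- **Outcome source.** The table in section 8b lists seizures, ASM dose and dates, date of progression and date of death among the items taken from the patient record. As far as the broken table can be read, they serve to correlate with hyperexcitability. No criterion for the epilepsy diagnosis is given, and the section does not say whether scEEG findings may enter the record.

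**The concern.** An accuracy estimate means what it claims only if the index test and the outcome are established independently. Two routes of dependence are open here.

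1. **Review bias.** A reader who knows that a patient has had a seizure or started ASM may be readier to accept a borderline flagged episode as an IED, and to reject one in a patient who is seizure-free.
2. **Incorporation bias.** If the clinician who decides on epilepsy has seen the IED findings, the predictor becomes part of the outcome.

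Either would raise agreement between IED status and epilepsy without IEDs predicting anything. The comparison affected is the only one the study is sized for. The first route cannot be repaired at analysis: once a reading has been made with the clinical course known, no statistical method makes it a masked one.

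**Working it through.** **1. The protocol's sample size.** Inputs from section 4a: null accuracy 0.5, one-sided 2.5%, power 80%, and 0.85 used as the accuracy under the alternative.

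n = [(1.960 × √(0.5 × 0.5) + 0.842 × √(0.85 × 0.15)) / (0.85 − 0.5)]² = 13.39, rounded up to 14.

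The stated figure reproduces and is not in dispute. It also confirms that the sized comparison is per-patient agreement between IED status and epilepsy.

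**2. The passages side by side.**

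| Question | What the protocol states |
|---|---|
| Who makes the IED call? | A neurophysiologist, on software-flagged episodes (3a) |
| Is the reader masked to clinical course? | Not stated |
| Is the recording used for anything besides IEDs? | Yes, detection of seizure activity (2b) |
| Where do seizure data come from? | The patient record (8b) |
| Are IED findings kept out of the epilepsy diagnosis? | Not stated |

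**3. Weight of one call.** 1/14 = 7.1 percentage points. The protocol names no test, so two are shown. Exact binomial: P(X ≥ k | n = 14, p = 0.5). Normal approximation: z = (k/14 − 0.5) / √(0.25/14).

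| Correct calls | Exact one-sided p | Normal-approximation z | One-sided p |
|---|---|---|---|
| 10/14 | 0.090 | 1.60 | 0.054 |
| 11/14 | 0.0287 | 2.14 | 0.016 |
| 12/14 | 0.0065 | 2.67 | 0.004 |

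The 2.5% line falls between 11 and 12 under the exact test, and between 10 and 11 under the normal approximation. A single call crosses it either way. This is the granularity of 14 patients, not a measure of bias.

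**4. Illustration with an assumed bias.** Let f be the share of truly discordant patients who become concordant through unmasked reading or diagnosis. The protocol gives no value, so f is an assumption. At true accuracy 0.50, apparent accuracy is 0.50 + 0.50 × f. The chance of declaring success is P(X ≥ k | 14, apparent accuracy).

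| f (assumed) | Apparent accuracy | k = 12 (exact rule) | k = 11 (normal rule) |
|---|---|---|---|
| 0 | 0.50 | 0.6% | 2.9% |
| 0.1 | 0.55 | 1.7% | 6.3% |
| 0.2 | 0.60 | 4.0% | 12.4% |
| 0.3 | 0.65 | 8.4% | 22.0% |

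Under the exact rule the nominal 2.5% is exceeded by f = 0.2. Under the normal rule it is slightly exceeded even without bias and rises quickly from there.

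**The case against.** **The outcome is already separate from the scEEG.** Section 8b names the patient record as the source for seizures, section 2b says ASM follows the first epileptic seizure, and section 3a places epilepsy care under national guidelines. This stands in part: a record-based endpoint appears to be intended. It does not close the gap, because a record entry may itself be prompted by the scEEG and no epilepsy criterion is given.

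**Silence on masking is not proof of unmasked reading, and a separate plan may cover it.** The first half is right, and the point claims only that no masking is stated. On the second half, the reading procedure is part of how the data are collected. Section 3a already describes it, and it has to be settled before the first reading.

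**IEDs occur between seizures, so sharing a recording is not in itself incorporation.** This is correct. No passage says that IEDs enter the epilepsy diagnosis, so incorporation bias is a possibility only.

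**The study is explorative.** True, but it specifies a null hypothesis, a significance level and a power for exactly this comparison.

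Two stronger readings are tempting and should not be drawn:
- *That the diagnostic and treatment role in section 2b contradicts section 3c* ("There will be no deviations from standard treatment both regarding tumor and epilepsy treatment"). The words on diagnosis and treatment optimization describe the device in general within a literature review. They can be true while patients in this study receive guideline care.
- *That 11 of 14 correct would not be significant.* This depends on choosing an exact test, which the protocol does not name. The normal approximation, which reproduces the 14, gives p = 0.016.

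**Conclusion.** The point holds as an open risk to the only sized comparison, not as a demonstrated bias. As written, the protocol lets the neurophysiologist make a judgement-based IED call with knowledge of the clinical course, and lets that call reach whoever decides on epilepsy. Review bias is the firmer of the two concerns, and incorporation bias is possible. Where present, both would be expected to raise apparent accuracy. The protocol does not allow the amount to be computed, and the table over f only shows sensitivity to an assumed value. What can be said without assumption is that one call is worth 7.1 percentage points and can decide the test under either of the two usual analyses. The conclusion rests on reading section 8b as a record-based source for seizures and on the absence of any masking statement in the protocol.

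**What to change.** Add to section 3a:

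1. The same neurophysiologist classifies the flagged episodes from coded files, without access to seizure, ASM, MRI or survival data. The calls are locked before they are linked to clinical data.
2. The epilepsy endpoint is established from the patient record without using the IED calls.
3. A sensitivity analysis reports accuracy with and without seizures known only from the scEEG. This avoids deciding in advance that such seizures must leave the main endpoint, which would be debatable given the stated purpose of better seizure detection.

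**Cost.** A few sentences in the protocol and slightly more data handling for coding and locking. No additional reader, patient or visit is needed.

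**Limit.** Masking does not settle whether IEDs recorded after the onset of epilepsy count towards the predictor. That is a separate question.

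### Section 4a tests diagnostic accuracy but assumes only sensitivity, so its inputs do not fix the power; even with accuracy taken as 0.85, 14 patients cannot meet both one-sided 2.5% and 80% power

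*Protocol*

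**What the plan says.** All the relevant text is in the protocol, section 4 (Statistical considerations), part a (Power analysis).

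- Sample size: "the number of patients needed for this study is estimated to be fourteen patients".
- Error rates: "The level of significance is 2.5% one sided and the power 80" per cent.
- Assumptions: "the proportion of patients having epilepsy is 50%, and the sensitivity for epilepsy with hyperexcitability is 85% or better".
- Hypotheses: "The null hypothesis is diagnostic accuracy = 0.5 against the alternative that diagnostic accuracy > 0.5".

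The section gives no specificity, no assumed value of overall accuracy and no test. It describes the study as explorative and says that power assumptions are hard to make because comparable data are lacking. Section 3a defines the marker as a yes/no finding: hyperexcitability is present if interictal discharges appear on the subcutaneous EEG.

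**The concern.** The assumption and the hypothesis concern different quantities. Sensitivity describes only the patients who develop epilepsy; accuracy also depends on how often the marker is negative in those who do not. A power statement for accuracy cannot be derived from sensitivity and prevalence alone.

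There is a second problem. With 14 binary outcomes, the attainable significance levels are far apart, and a large-sample formula may give a sample size at which the nominal level and the nominal power do not hold together.

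This is the only hypothesis that the protocol sizes, and it is the stated reason for choosing 14 patients. If the power is materially below 80%, a non-significant result says less about the marker than the protocol suggests.

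**Working it through.** **Inputs, all from section 4a.** n = 14; one-sided alpha = 0.025; power = 0.80; proportion with epilepsy = 0.50; sensitivity = 0.85 (the lower end of what is assumed); null accuracy p0 = 0.5. Specificity is not given.

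**Step 1: reproduce the 14.** One-sample proportion, normal approximation, p0 = 0.5, with p1 = 0.85 entered as the accuracy:

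n = [(1.96 × √(0.5 × 0.5) + 0.8416 × √(0.85 × 0.15)) / (0.85 − 0.5)]²
= [(0.980 + 0.3005) / 0.35]² = 13.39, rounded up to 14.

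The approximate power at 14 is 82.2%. The arcsine version gives 13.05, also 14. So the stated size can be recovered, provided that 0.85 is used as the accuracy.

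**Step 2: what that requires.** Accuracy = 0.5 × sensitivity + 0.5 × specificity = 0.425 + 0.5 × specificity. Accuracy of 0.85 therefore needs specificity = (0.85 − 0.425) / 0.5 = 0.85. Without a specificity, sensitivity of 85% is compatible with any accuracy from 0.425 (specificity 0) to 0.925 (specificity 1).

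**Step 3: level and power at n = 14 and accuracy 0.85.** Let X be the number of patients correctly classified, treated as binomial.

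- Reject at X ≥ 12. Alpha = (91 + 14 + 1) / 16,384 = 106 / 16,384 = 0.0065. Power = 91 × 0.85¹² × 0.15² + 14 × 0.85¹³ × 0.15 + 0.85¹⁴ = 0.291 + 0.254 + 0.103 = 0.648.
- Reject at X ≥ 11. Alpha = (364 + 106) / 16,384 = 470 / 16,384 = 0.0287. Power = 0.648 + 364 × 0.85¹¹ × 0.15³ = 0.648 + 0.206 = 0.853.

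The z test behind step 1 uses the second rule: at 11 of 14, z = (0.7857 − 0.5) / (0.5 / √14) = 2.14, above 1.96. No cut-off lies between 11 and 12, so a non-randomised test on the count either keeps 2.5% with 65% power or reaches 80% power with a level above 2.5%.

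**Step 4: dependence on specificity.** Sensitivity held at 85%:

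| Specificity | Accuracy | Power, ≥ 12/14 (alpha 0.65%) | Power, ≥ 11/14 (alpha 2.87%) |
|---|---|---|---|
| 70% | 0.775 | 36% | 61% |
| 80% | 0.825 | 55% | 78% |
| 85% | 0.850 | 65% | 85% |
| 90% | 0.875 | 75% | 91% |
| 95% | 0.900 | 84% | 96% |
| 100% | 0.925 | 92% | 98% |

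Under the rule that keeps 2.5%, 80% power needs accuracy of about 0.888, that is, specificity of about (0.888 − 0.425) / 0.5 = 93%.

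**The case against.** The best defence is that the protocol names no exact test, and that 14 comes from a standard formula. The matching z test has true power of 85% at accuracy 0.85, so 80% is reached; only the level slips, from 2.5% to 2.87%. The choice of test could be left to an analysis plan, and the study calls itself explorative.

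Much of this stands. A reader might infer that section 4a contains a slip in arithmetic, or that the 80% is simply not delivered. The documents do not support that: the figure reproduces, and the 65% applies to a test that keeps strictly to 2.5%. A reader might also infer that the study has at least a one-in-three chance of missing a marker as good as assumed. That does not follow either. Specificity is unstated, so 85% is not a ceiling, and power is 75% at specificity 90% and 84% at 95%. The protocol also allows sensitivity above 85%, which would raise power further. Nothing in the documents shows that specificity will be low; section 3a provides for review of software-flagged discharges by a clinical neurophysiologist.

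The defence does not answer the mismatch of parameters. Whatever test is used, specificity is needed to get from the stated assumption to the stated hypothesis, and even the 11-of-14 rule falls below 80% at specificity 80%. Nor does the explorative label help: having stated a level, a power and a null hypothesis, the section should make them agree.

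**Conclusion.** The point holds in two parts. The firmer one is that the inputs in section 4a do not determine its power, because accuracy is tested and only sensitivity is assumed. The second is that, with the implied specificity of 85% granted, the stated 2.5% and 80% cannot both hold at n = 14: the choices are 65% power at alpha 0.65%, or 85% power at alpha 2.87%. The effect of the missing specificity is the larger: over 70% to 95%, power under the 12-of-14 rule runs from 36% to 84%.

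These figures assume 14 evaluable patients, a binomial count of correct classifications, 50% with epilepsy and sensitivity of exactly 85%. The specificity values are illustrative, since the protocol gives none.

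**What to change.** Restate section 4a with the assumed specificity (or overall accuracy), the test and its cut-off. For example:

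> With 14 evaluable patients the exact one-sided 2.5% binomial test rejects at ≥ 12/14 correct (attained alpha 0.0065); power is 65% if sensitivity and specificity are both 85%.

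Add a short table of power over specificities below and above 85%, such as the 12-of-14 column in the working.

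The cost is one reworded paragraph and a less favourable power figure; no extra patients are needed. Enlarging the sample would not replace the restatement. With 15 patients (reject at ≥ 12, alpha 0.0176) power is 82% only if specificity is also 85%; it is 74% at 80% and 55% at 70%.
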